Power: Sample sizes were calculated to provide sufficient power to calculate differences in our primary outcome (CR adherence, as measured by % completing 30+ sessions) between the control condition and any of the three intervention conditions as well as between the combined intervention and either of the interventions delivered alone. Of most relevance, preliminary data from a previous trial on the use of incentives to increase CR rates among lower-SES individuals show that 54% of those receiving incentives completed the 30+ sessions compared to 28% of those receiving usual care. Using these proportions and the likelihood ratio test for two proportions in SAS POWER, 57 individuals per condition would be needed to detect a significant difference between conditions with 80% power. A seminal set of studies, conducted by Co-I [name], that systematically determined the efficacy of case management and incentives, alone and in combination, on cocaine abstinence, provided additional data for the power estimates.⁵⁴⁻⁵⁸ Using effect sizes from these five studies, the maximum estimated number of participants needed per condition is 50 to detect a significant difference in treatment adherence in combined intervention vs. single intervention with 80% power. Comparing any of the interventions singly or combined to usual care at four months post-treatment is estimated to require at most 25 participants per condition. Supporting these estimates, additional studies on the use of case management or incentives for adherence to other health-related behaviors have demonstrated effect sizes comparable to the studies referenced above.^{66,67,73,106,107} As such, the proposed sample size of 209 randomized subjects (57/intervention condition, 38 control) will allow us to conduct all pre-planned pairwise comparisons of the primary outcome measure (program adherence) with 80% power.

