Note: Only those individuals authorized to solicit consent may sign the consent form confirming that the prospective subject was provided the necessary information and that any questions asked were answered.

Patients who are hospitalized, or being cared for, due to a recent cardiac event and are enrolled in Medicaid, or have less than a high school education will be approached for possible inclusion by the PI or a trained representative. Patients will be given an unlimited amount of time to decide about participating in the study. A consent form with appropriate HIPAA language will be used for this study. Patients will have the option of electronic consent or consenting in person. UVM Staff will email a unique link to a redcap survey. We will go through the consent form verbally over the phone and the patient will have an opportunity to ask any questions they may have prior to consenting to be in the study.

Information Withheld From Subjects: Will any information about the research purpose be withheld from potential or participating subjects? If so, explain and justify the non-disclosure and describe plans for post-study debriefing.

Not applicable

Statistical Analysis Plan

Sample Size and Power

Sample sizes were calculated to provide sufficient power to calculate differences in our primary outcome (CR adherence, as measured by % completing 36 sessions) between the control condition and any of the three intervention conditions as well as between the combined intervention and either of the interventions delivered alone. Estimates were based on a series of studies conducted within our research group.

Of most relevance, preliminary data from our prior trial on the use of incentives to increase CR rates among lower-SES individuals showed 54% of those receiving incentives completed the 36 sessions compared to 28% of those receiving usual care. Using these proportions and the likelihood ratio test for two proportions in SAS POWER, 56 individuals per condition would be needed to detect a significant difference between conditions with 80% power.

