In the literature, studies on the use of case management or incentives for adherence to other health-related behaviors have demonstrated effect sizes comparable to the studies referenced earlier,^{66,67,106,107} providing additional evidence that those prior studies are appropriate for estimating sample sizes for the proposed study. Thus, we estimate that 57 participants per treatment condition (i.e., case management only, incentives only, and case management with incentives) and 38 participants in the usual care condition will allow us to conduct all pre-planned pairwise comparisons of the primary outcome measure (program adherence) with 80% power.

Randomization

Stratified random allocation of participants will be used to assign individuals to conditions, using two dichotomous variables to stratify the sample: age (<57 years of age vs. ≥ 57) and smoking status (current smoker vs. former/non-smoker). Age and current smoking were the two demographic variables which significantly predicted CR attendance in the prior trial. As median age in our prior trial was 57, and 40% of participants were current smokers, stratifying using the proposed cut-offs will result in randomization cell sizes of appropriate size. Participants will be allocated to conditions using a 3:3:3:2 routine, whereby for every three individuals assigned to one of the three treatment conditions (case management only, incentives only, and case management plus incentives), two individuals will be assigned to the control condition (usual care). Assignment of participants to conditions will be conducted using the stratified block design method¹⁶³ in the

Interactive Voice Recognition (IVR) system maintained by the Medical Biostatistics Unit at the University of Vermont. Using this system will allow us to allocate participants over time, as they become eligible, while still maintaining desired arm counts across conditions.

Primary and Secondary Data Analyses

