By definition, primary outcome data will not be missing since it focuses on program participation. For other variables, minor amounts of missing data, due to factors other than dropout from the CR program, will be ignored, leading to deletion of cases in regression analyses. However, if substantial amounts of missing data of key predictor variables exist, we will explore the randomness of missing data using Little's MCAR (missing completely at random) test in SPSS 24. If we cannot reject the null hypothesis, we will proceed to use multiple imputation procedures in SAS 9.4 (PROC MI and PROC MIANALYZE) to generate results based on imputed data.

Although this study is powered for our primary outcome of adherence to CR, we will also carefully examine improvements in fitness, and other health outcomes (quality of life, maximal exercise capacity, weight, waist measurements) between conditions, using the pre-planned comparisons outlined for the primary outcome. Additionally, we will examine changes in executive function measures and socio-cognitive status at 4 and 12 months. Changes in these scores will also be examined for possible gender interactions. Since multiple observations for each participant will be obtained, the general analytic approach will consist of analysis of covariance (ANCOVA) at 4 months and repeated measures analysis of variance (ANOVA) at 12 months. Formal testing will examine the condition by time interaction term to assess differential time changes between treatment conditions. Post-hoc comparisons between conditions will be made if significant interactions are observed.

Survival analyses will be conducted once all participants have completed the 36 sessions of their CR program (or, alternatively, have dropped out of the program). Preliminary analyses of all other outcome measures will occur upon collection of all 4-month measures across all participants. Final analyses of secondary outcome measures, using repeated measures procedures, will be conducted upon collection of all 12- month measures across all participants. Across all tests, statistical significance will be defined as $p < 0.05$ (2-tailed).

Cost Effectiveness Analyses

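### For the secondary outcomes, the plan specifies no baseline-adjusted 12-month contrast and makes between-arm comparisons conditional on an omnibus condition-by-time test

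*Combined protocol and SAP*

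**What the plan says.** The protocol (Statistical Considerations, Data Analysis) and the SAP (Primary and Secondary Data Analyses) carry the same paragraph on secondary outcomes. The general approach is "analysis of covariance (ANCOVA) at 4 months and repeated measures analysis of variance (ANOVA) at 12 months". The test is then defined: "Formal testing will examine the condition by time interaction term to assess differential time changes between treatment conditions". Comparisons between conditions are described as post hoc and follow only when an interaction is significant. Earlier in the same paragraph, fitness and the other health outcomes are to be examined with the comparisons already laid down for the primary outcome: each intervention against usual care, and the combined intervention against each single one. That makes five contrasts.

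The SAP adds that the final secondary analyses, once all 12-month data are in, use repeated measures procedures. The protocol's Study Design section lists executive function, fitness and quality of life at one year among the secondary outcomes, and its Study Measures section sets assessments at baseline, four months and one year.

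The documents do not name the covariate in the 4-month ANCOVA. They do not say whether baseline enters the 12-month model as a level of time or as a covariate, or at which visit the post-hoc comparisons are made.

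**The concern.** One-year differences in fitness, quality of life and executive function are declared targets, but the plan defines no estimate for them. Three things follow.

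- The method changes between visits, apparently from one that conditions on baseline to one that works through change from baseline. In a randomised trial the second is less precise.
- The test that opens the way to comparisons pools all visits. A positive result need not mean that the arms differ at one year.
- The paragraph gives two instructions, pre-planned pairwise contrasts and comparisons conditional on an interaction, without saying how they fit together. Two analysts could follow it and report different things.

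At stake are wider one-year intervals than the data allow, and a 4-month effect being read as a lasting one.

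**Working it through.** **The plan's own figure.** The only sample-size calculation concerns the primary outcome. For 54% against 28%, two-sided 0.05, likelihood ratio test, power is Φ(δ√N − 1.96), where δ² is twice the arm-weighted mean of p·ln(p/p̄) + (1−p)·ln((1−p)/(1−p̄)). With p̄ = 0.41, δ² = 0.0708. At 56 per arm, N = 112, δ√N = 2.816 and power is 0.804; at 55 it is 0.797. So the SAP's "56 individuals per condition would be needed to detect a significant difference between conditions with 80% power" reproduces, and the protocol's 57 (power 0.811) is one more. Arm sizes are 57, 57, 57 and 38, and 3 × 57 + 38 = 209. No SD, correlation, effect size or power is stated for any secondary outcome.

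**Precision at 12 months.** From the documents: 57 against 38 and two-sided 0.05. Assumed: equal variances at baseline and 12 months, complete data, and baseline-to-12-month correlation r. In SD units the 95% half-width is 1.96 × √(1/57 + 1/38) × k = 0.410 × k, with k = √(1 − r²) for ANCOVA and k = √(2(1 − r)) for the change contrast. Their ratio is √(2/(1 + r)). The share of participants whose information is lost is 1 − (1 + r)/2.

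| r (assumed) | ANCOVA | Change | Change wider by | Equivalent loss of participants |
|---|---|---|---|---|
| 0.4 | 0.376 | 0.450 | 20% | 30% |
| 0.5 | 0.355 | 0.410 | 15% | 25% |
| 0.6 | 0.328 | 0.367 | 12% | 20% |
| 0.7 | 0.293 | 0.318 | 8% | 15% |
| 0.8 | 0.246 | 0.260 | 5% | 10% |

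The ratio does not depend on arm sizes, so it also holds for 57 against 57.

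**What the interaction tests.** Randomisation makes the expected baseline difference zero. Let an arm's differences from usual care be 0, d4 and d12 at the three visits.

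- Baseline as a level of time: the null hypothesis is 0 = d4 = d12 for every arm, with (4 − 1) × (3 − 1) = 6 degrees of freedom. It is false whenever d4 is not zero, even if d12 = 0.
- Only 4 and 12 months as levels: the null hypothesis is d4 = d12. A sustained effect satisfies it.

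**Simulation.** 4,000 trials per scenario with arms of 57/57/57/38, equal correlation r between visits, complete data, and an assumed effect of 0.5 SD in all three intervention arms. Entries are rejection rates; contrasts are combined intervention against usual care at 12 months.

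| Scenario | r | Interaction, 3 visits | Interaction, 4 and 12 months only | ANCOVA | Change | Change, gated by 3-visit interaction |
|---|---|---|---|---|---|---|
| Effect at 4 months only | 0.5 | 66% | 63% | 5% | 5% | 4% |
| Effect at 4 and 12 months | 0.5 | 66% | 5% | 78% | 66% | 53% |
| Effect at 4 and 12 months | 0.7 | 89% | 5% | 92% | 87% | 81% |

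**Illustrative power.** If an effect is chosen so that ANCOVA has 80% power, the change contrast has Φ(2.802/ratio − 1.960). At r = 0.5, 2.802/1.155 = 2.426, giving 68%. At r = 0.6, 2.802/1.118 = 2.506, giving 71%. At r = 0.7, 2.802/1.085 = 2.583, giving 73%.

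**The case against.** Repeated measures ANOVA with a condition-by-time test is conventional, and its contrasts are unbiased under randomisation with complete data. Only secondary outcomes are involved. The precision loss depends on a correlation that the documents do not give, and it need not be the same for weight, peak oxygen uptake and questionnaire scores; at r = 0.9 it is about 3%. The omnibus test is not always the weaker one. With a sustained 0.5 SD effect in the combined arm alone, the three-visit interaction rejected in 81% of simulated trials at r = 0.5, against 79% for the 12-month ANCOVA contrast. All of this stands, and it limits the point to an efficiency gain and a clarification.

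Three stronger readings are tempting, and the documents do not support them.

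- A reader might infer that baseline adjustment is dropped at 12 months. The 4-month covariate is not named, so baseline adjustment there is itself an inference. If baseline is a level of time at 12 months, it is still used, only less efficiently.
- A reader might infer that the 12-month difference is never tested. With baseline as a level, a 12-month difference contributes to the interaction, comparisons follow a significant result, and pairwise comparisons are already promised for fitness and health outcomes. What is missing is a named 12-month contrast that does not depend on the gate.
- A reader might infer that the trial loses stated power. The plan says it is powered for adherence and claims none for these outcomes.

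**Conclusion.** The point holds as a free improvement to the secondary analyses. The switch of method, the omnibus test and the conditional comparisons are all in the text, and they sit uneasily with the pairwise comparisons promised in the same paragraph.

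On the natural reading of the 12-month model, intervals are about 20% to 5% wider than with ANCOVA for correlations of 0.4 to 0.8. This assumes equal variances and baseline as a level of time. A significant interaction does not establish a one-year effect, because 4-month differences alone can produce it. Under the alternative reading, with 4 and 12 months only, a sustained effect is rejected no more often than chance. Both statements follow from the null hypotheses and do not depend on the correlation; the simulated rates do, and on the assumed effect size. The fall from 80% to 68%, 71% or 73% is illustrative only. The primary adherence comparison is untouched.

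**What to change.** In both places (protocol, Data Analysis; SAP, Primary and Secondary Data Analyses), replace the 12-month repeated measures ANOVA with a mixed model for the 4- and 12-month values. Include baseline value, condition, visit, condition-by-visit and baseline-by-visit, with unstructured covariance. Estimate the five pre-planned contrasts with 95% confidence intervals at each visit, not gated by the interaction, and state that the 12-month contrast is the one-year test. Name the baseline value as the covariate in the 4-month ANCOVA. Bring the SAP sentence on final secondary analyses into line.

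ANCOVA at 12 months is a simpler alternative, but equivalent only when follow-up is complete. The mixed model also uses the 4-month values of participants with no 12-month value. Gaps are foreseeable: the protocol says several executive function tasks will not be collected when in-person visits are not allowed.

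The cost is wording; baseline values are already collected. Two consequences should be accepted openly. Participants without a baseline value drop out of the model, as they would from a complete-case ANOVA. Removing the gate also gives up the limited protection of a global test when no arm differs. The plan sets every test at 0.05 with no adjustment, so these contrasts should be presented as secondary estimates with their intervals.
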